Problem Solving is strongly promoted by VA Mental Health Service Line. That group has conducted pilot studies looking at rolling out PST in that context; but they have communicated to us an interest in evaluating problem solving in physical health as well. [name] ongoing work with with VA problem solving leaders (ie, [name], VA Senior Consultant/Liaison for Psychological Health, (59)) will allow us to inform them on the potential use of problem solving in prevention, and will also allow us to implement this aspect of our intervention with relative ease.

Group Visits have been mandated by VA as part of PACT (60). They are thought to represent an efficient means to provide access to high-quality care, and there is evidence that they meet that goal for patients with serious chronic illness, including in the VA (11, 61-63). However, group visits for patients without severe or symptomatic chronic illness have not been studied well. This proposal allows PACT to determine the role of group visits for relatively healthier patients; it may define the limits of the group model in VA, or allow VA to confidently expand group care to a much wider range of patients.

D. RESEARCH DESIGN AND METHODS

D.1 Study Design. We propose a randomized, controlled trial (RCT) of our GPC intervention (details in section D.5 below). Outcomes will be measured at baseline, 6, and 12 months after enrollment. The control group will receive usual care.

D.2. Setting. We will perform the study among patients at the Durham and Buffalo VAMCs. Multiple VAMC settings are used to increase generalizability, and to increase numbers of eligible patients. [name], key personnel on this grant, is core faculty of a VA Mental Health Center of Excellence, the VISN 2 Center for Integrated Healthcare (CIH). The goal of CIH is to integrate behavioral health into primary care. The center has numerous research projects ongoing at all times; research personnel at CIH are on staff at Buffalo VAMC. Buffalo will be treated as an equal site for the scientific protocol, with the goal of approximately equal enrollment from Buffalo and Durham.

D.3. Patients. The patients will be 400 VA users (see enrollment feasibility, D.3.c.v, and sample size, D.9, below) without prior history of cardiovascular event, but with at least 5% risk of such an event, with at least 2% of that risk potentially reversible.

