D.3.a. Framingham Risk Score. FRS (64) is calculated using age, gender, blood pressure, total and HDL cholesterol, smoking status, diabetes status, and status of taking blood pressure medication; we are excluding diabetic patients (see D.3.a.ii below). As such, all patients in the study will have hypertension with less-than-optimal control, **OR** elevated total cholesterol, **OR** be a current smoker. The table shows some typical FRS risk profiles. The examples are all male non-smokers:

	Subject A1	Subject A2	Subject B1	Subject B2	Subject C1	Subject C2	
Age	50	50	55	55	55	55	
SBP (on med)	-	-	-	-	140	-	
SBP (no med)	135	135	160	140	-	140	
Total cholesterol	210	190	190	190	190	190	
HDL	35	45	45	45	45	45	
10 yr FRS	7%	5%	9%	7%	9%	7%	

D.3.b. Rationale for 5% risk, with 2% reversibility. We are targeting a group of primary prevention patients that are relatively sick for primary prevention. A 2% reversibility is chosen because this is approximately the effect size seen in our study of a similar intervention among non-VA users; 5% baseline risk is chosen because patients with lower risk than this likely will not justify this relatively intensive intervention (nor, often, have 2% reversibility).

D.3.c. Process for identifying eligible patients. We will use a multi-phase process to identify patients that fit this demographic, reviewing aggregated local CPRS data first, then reviewing individual charts, then interviewing patients and obtaining lab data. We will target enrolling 200 from each site (Durham and Buffalo).

D.3.c.i Accrual of potential eligible patients from database: Patients will be initially identified from local VA administrative data (or VINCI, depending on VA policy at that time). In the database phase, identification will use the following inclusion and exclusion criteria:

 Inclusion: a diagnosis of inadequately controlled hypertension, as defined by an outpatient ICD-9 code of 401.x and a most recent blood pressure with either systolic > 140 mmHg or diastolic > 90 mmHg, **OR** (2) inadequately controlled dyslipidemia, as defined by most recent total cholesterol > 200 mg/dl **or** HDL cholesterol < 35 mg/dl, **OR** (3) current smoking, which can be identified using the CPRS Health Factor tied to the smoking clinical reminder. Medication-taking status for these illnesses is neither required nor excluded.

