Once patients have completed the measurement battery and blood draw, we will prepare to randomize them to receive or not receive the GPC intervention. To maintain blinding, patients will be randomized remotely from the enrollment, and the blinded research assistant will not provide the assignment. Instead, the research assistant will obtain a date, time, and working phone number for a randomization phone call to be made (within 3 business days) by the research assistant from the other site (Durham vs. Upstate New York). This delayed randomization is also required in order to allow lipid testing to be completed, so that patients with a baseline FRS of < 5%, or lack of reversible risk, may be excluded. *To maintain subject engagement, intervention patients will be mailed "Moving Forward," a VA-approved primer on Problem-Solving, after randomization (see D.4.a below).*

Participating individuals will be followed for 12 months. The intervention lasts only 6 months; however, patients are in theory being taught lasting skills in the intervention. It is therefore an important question to determine if the effects of the intervention (if any) extinguish after contact with the program ends. The local RA will ascertain the measurement battery at baseline, 6, and 12 months. At all follow-up visits, the RA assigned to measure outcome variables will be blinded as to which group the patient is randomized. Patients will receive \$50 compensation for each scientific visit, for a total maximum of \$150 for the scientific visits.

D.4.z. Pilot Study. The first 10 patients enrolled into the study will be part of a pilot cohort. They will not be randomized; instead, all 10 will be assigned to the intervention (section D.5 below). These patients will have the same patient experience as patients randomized to the intervention arm (D.4.a below). This is being done to determine if the intervention needs modification prior to implementation in the study. These patients will sign a separate, clearly marked consent form notifying them that they are in a pilot study; however, the risks of the pilot are essentially identical to the risks of the planned trial.

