The phone interventionist will receive formal training in MI; we have purchased this service from a local MI teacher for numerous other personnel on other successful protocols (25). S/he will also receive training in coaching from professional coaches at Duke University Medical Center (3).

[name], who is the investigator with experience in problem solving (see budget justification for credentials) will supervise the interventionists. *To assure fidelity, all intervention group sessions and phone calls will be recorded, and those that are randomly chosen to be overheard by [name] will be overheard after they occur.* This eliminates a Hawthorn Effect for behavior of the interventionists when they know they are being observed. Second, we will establish checklists for both behaviors addressed and Problem-Solving approaches used in each session so we have a summative evaluation of intervention fidelity. **D.8. Measures.**

D.8.a. Primary Outcome Variable. The primary outcome is Framingham Risk Score, which yields a probability of major cardiovascular event over the next 10 years as its output (64). The inputs to FRS are: age; gender; diabetes status (which will be 0 at baseline for all enrolled patients); total and HDL cholesterol, which will be measured directly by standard VA laboratory methods; smoking status, measured by self-report; use of blood pressure medications, measured by VA medical record and self-report, and systolic blood pressure. All components of the FRS will be measured at each study visit. At each visit, two measurements of blood pressure, taken seated after a 5-minute rest and at 5-minute intervals, will be obtained. The final outcome will be the average of the two measures. All BP measurements will be performed using electronic blood pressure cuffs (148). Study personnel will be trained in measurement technique using established methods (149).

D.8.a.i. Justification for primary outcome. Patients in the intervention arm may choose one of a number of behaviors to work on, with no obvious common outcome across all potential behaviors (for example, someone who quits smoking has probably improved her/his cardiovascular risk even if s/he gains 10 pounds). Thus, a direct measure of risk is needed, and FRS is the best validated of these. Also, we have experience with successfully improving FRS in coaching interventions (3).

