second question on current smoking (in the last 7 days) from the Behavioral Risk Factor Surveillance System (BRFSS) ³⁹Alcohol Use Disorders Identification Test (AUDIT-C)⁴⁰: a 3 question alcohol screen that can help identify hazardous drinkers for those with active alcohol use disorders (including alcohol abuse or dependence). Physical Activity (Exercise Vital Sign)⁴¹: Two questions to measure days and minutes per day an individual engages in moderate to strenuous exercise. Pain: Three questions on the number of days pain interfered with your life within the past 30 days (question from the CDC HRQOL Healthy Days Symptoms Module⁴²), the amount of pain today (EuroQol EQ-5D-5L ⁴³), and pain intensity (VA numeric rating scale from 0 no pain to 10 worst pain imaginable⁴⁴) Sleep: 4 questions assessing quality of sleep

D.9. DATA ANALYSIS.

D.9.a. Descriptive statistics. Descriptive statistics, including graphical displays, will be used to summarize all study variables overall and by intervention arm. Evidence of imbalance in baseline characteristics will be noted and discussed as to whether they are clinically significant. As recommended by CPMP guidelines (80), we will consider sensitivity analyses adjusting for these baseline characteristics to ensure that an observed intervention effect is not due to this baseline imbalance. We will construct individual and mean trajectory plots of the longitudinal outcome variables (e.g., FRS) to understand their general trends over the study period. In addition, we will explore the variability and correlation structure of the longitudinal outcome variables. All statistical analyses will be performed using the SAS software package; the Durham HSR&D COE maintains the current SAS release on our system.

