Studio Visual Basic Net. On the laptop, data will be stored in a series of XML files until daily synchronization with the Illume server. We have chosen DatStat Illume 4.7 because of industry standard acceptance as a reliable and flexible method for collecting and storing research survey information. All data collected can be exported into a number of standard formats including SAS, MS Access, and SQL Server. Server data will be backed up on a daily basis as well. We have used similar methods of data entry in our prior studies.

D.10.b. Data Quality. Use of the above electronic data management system will aid the research assistant (RA) conducting study visit to monitor which data collection instruments and questions have been completed by the patient. Though the computerized auditing procedure, the RA will determine if all questions have been answered. If not, the subject will be given the opportunity to answer questions. As with all study components, the study patient will have the opportunity to decline to answer any questions. Before the end of the study visit, the RA will complete a checklist to ensure that all measurements are completed.

Study implementation and quality assurance methods that we will be employed include: 1) careful scheduling and timely monitoring of the planned visit schedule to be certain that complete visits do occur; 2) collection of contact information for each patient at each visit; 3) prompt rescheduling of missed study visits; and 4) review and documentation of the reasons for missed visits that do occur. We will also review individual patient data promptly to identify problems or missing values that can be completed by follow-up.

D.10.c. Masking Procedures. All personnel will be unblinded to arm assignment EXCEPT (1) the Research Assistant gathering outcomes data, and (2) [name]. The purpose of keeping [name] blinded is to have him available to resolve issues regarding individual patients, where knowledge of arm assignment might compromise the unbiased nature of the decision. The purpose of unblinding [name] is to allow him to use clinical judgment regarding adverse events or other clinical situations.

E. DISSEMINATION AND IMPLEMENTATION

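### Does the primary outcome need a written rule for when the VA record and self-report disagree on blood pressure medication?

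*Combined protocol and SAP*

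**What the plan says.** D.3.a makes "status of taking blood pressure medication" one of the FRS inputs. D.8.a says where each input comes from: the laboratory for cholesterol, self-report for smoking, the average of two readings for systolic pressure, and for medication "use of blood pressure medications, measured by VA medical record and self-report, and systolic blood pressure". It adds: "All components of the FRS will be measured at each study visit". No section says which medication source prevails. The source list under Protection of Human Subjects (A.2) places medications under the electronic record only, but it is an inventory and sets no precedence.

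The score is also used at entry. D.3 asks for patients "with at least 5% risk of such an event, with at least 2% of that risk potentially reversible". D.4 delays randomization until lipids are back, "so that patients with a baseline FRS of < 5%, or lack of reversible risk, may be excluded", with the randomization call due within 3 business days.

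On blinding, D.4 has the local research assistant collect the measurement battery at baseline, 6 and 12 months, blinded to arm at follow-up. D.10.c states: "All personnel will be unblinded to arm assignment EXCEPT (1) the Research Assistant gathering outcomes data". The other exception is one named person, kept blinded so as to be "available to resolve issues regarding individual patients, where knowledge of arm assignment might compromise the unbiased nature of the decision". D.4.a has the project statistician hold the randomization sequence.

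**The concern.** Medication is the only FRS input with two named sources, and the plan does not say how to combine them. At least four readings fit the text: record, self-report, either, or both. In the D.3.a table, subjects C1 and C2 share age, systolic pressure, total cholesterol and HDL. They differ only in whether the pressure was taken on medication, and they score 9% and 7%. In that patient the flag is worth as much as the whole 2.0-point target difference.

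Two things could be at stake. A patient just under 5% could be eligible by one source and ineligible by the other, so two sites might decide alike cases differently. And if the choice of source were left until FRS is derived for analysis, the general wording of D.10.c suggests that the person choosing could know the arms and could, in principle, prefer the reading with the better result.

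**Working it through.** **The plan's own figure.** Sample Size Calculations (the second section numbered D.9.e) uses SD of change 6.3, ICC 0.03 and groups of 10 in the GPC arm only. The design effect is 1 + 9 × 0.03 = 1.27.

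- n per arm = (1.960 + 0.842)² × 6.3² × (1 + 1.27) / 2.0² = 176.8, so 177; the plan states 180.
- Standard error at 180 per arm = 6.3 × √(2.27/180) = 0.707; power for 2.0 points = 80.7%.

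**Size of the flag.** C1 − C2 = 9 − 7 = 2 points. Whole-percent rounding allows 8.5 − 7.5 = 1 to 9.5 − 6.5 = 3.

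**Entry.** Treat the flag as a constant hazard ratio over a short step (assumption): ln(0.91)/ln(0.93) = 1.30.

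- An unflagged 4.0% becomes 1 − 0.96^1.30 = 5.2% (4.5% to 5.9% with rounding).
- The unflagged score that just reaches 5% is 1 − 0.95^(1/1.30) = 3.9%. The affected band is about 3.9% to 5.0%.
- With the planning distribution (mean 29%, SD 14%, taken as normal), about 0.7% of patients fall in that band. With 20% disagreement, 400 × 0.007 × 0.20 = 0.6 patients. A sample closer to the D.3.a profiles would have more.

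**Noise in the arm contrast.** Suppose a fraction q of patients, equal in both arms, have their change shifted by 2 points. The SD becomes √(6.3² + 4q): 6.316 at q = 5% and 6.363 at q = 20%. Power is 80.5% and 79.9%.

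**Choice among the four readings.** The simulation used 180 per arm, the planning SD and ICC, no true effect, and half of patients on a drug with no true change. The sources disagreed with probability d at each visit, equally in both arms and independently across visits. There were 12,000 trials per setting and the flag was worth 2 points.

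| d (assumed) | Mean gap, highest to lowest contrast | 95th percentile | At least one of four readings has p < 0.05 |
|---|---|---|---|
| 5% | 0.07 | 0.14 | 5.6% |
| 10% | 0.10 | 0.20 | 5.9% |
| 20% | 0.14 | 0.28 | 6.5% |

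Each single reading rejected in 4.9% to 5.3% of trials. The last column is reached only by computing all four versions and reporting whichever is significant, which the plan does not do. Independent redrawing also exaggerates the gaps: an unused prescription or a non-VA drug tends to persist, and a constant error largely cancels in change from baseline. If 80% of patients keep the same source status (assumption), the gaps fall to 0.03, 0.05 and 0.06 points and the best-of-four rate is about 5.5%.

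**Who would choose.** D.4 requires a baseline score before randomization, so conflicts at entry have to be settled while no arm exists. D.4 and D.10.c then have a blinded assistant collect the same battery at months 6 and 12. For an informed choice to enter, a working convention would have to be dropped after baseline by someone who knows the arms. No section describes that.

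**The case for a change.** The strongest case for a change is that a primary outcome should have a complete written derivation before anyone who knows the arms could have to choose, and that one sentence would supply it. The omission stands out because D.8.b.iv does say what to do when two heights or two weights differ.

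The 2-point value may also be low. It comes from a patient at 7% to 9%, whereas the sample size rests on a baseline mean of 29%. If the hazard ratio of 1.30 held there, the flag would be worth (1 − 0.71^1.30) − 0.29 = 0.07, about 7 points (3 to 11 with rounding). The gaps between readings would then be 0.25, 0.36 and 0.49 points and the best-of-four rate about 7% to 9%. The noise would matter more too: at q = 20% the SD would be √(39.69 + 0.20 × 49) = 7.03 and power about 72%.

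The mixing of risk levels is a fair criticism, and the size is uncertain for that reason. It does not change the conclusion. With equal disagreement and no true effect, any one reading has the same distribution in both arms whatever the flag is worth, so its error rate stays nominal. Naming one source would not remove that source's own errors, so it would not recover lost power.

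A net difference between arms in the share of misclassified patients would bias the contrast by the flag value times that share: 0.2 points for 10 percentage points at 2 points per patient, 0.7 at 7. Nothing in the document points to such a difference, and a precedence rule would not prevent it. Self-report comes from patients who know their arm; the record counts prescriptions that are not taken. Real starts and stops of medication are a separate matter. They belong to FRS as defined, and D.9.a already provides that descriptive statistics "will be used to summarize all study variables overall and by intervention arm".

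The blinded person in D.10.c is a partial safeguard: the role covers decisions on individual patients but is not expressly assigned to this one.

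**Conclusion.** D.8.a leaves a real but small gap, of the kind a study team closes when it builds the data dictionary. The score has to be computed before the first patient is randomized, so a convention must exist before any arm does. Carrying it through months 6 and 12 is the natural reading of a plan in which one blinded assistant collects the same battery each time. On that reading the type I error stays near 5% and the planned comparison is sound. At entry the effect is confined to unflagged scores of about 3.9% to 5.0% and precedes randomization, so it touches reproducibility of eligibility and not the treatment effect.

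This rests on three assumptions: disagreement is similar in the two arms; one convention is used throughout; and the flag is worth roughly 2 points in typical patients. The last affects only the size of the gaps between readings. Neither source is clearly better, so prescribing one would not clearly improve any result. Recording the chosen convention is good housekeeping, but the plan does not need to change for it.
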